Known or predictable factors that may impair outcomes and interpretation of outcomes

A different therapy standard between participating centers and/or within the same center can lead to very variable outcomes between one patient and another, all other conditions being equal. This problem is tackled by indicating in detail the therapy to be followed depending on the type of lesion.

An incorrect recording of photographic images does not make it possible to determine the area of the lesion via software. This problem is tackled by providing precise instructions on the correct use of the tools available for the retrieval of images.

Discontinuity of patients can affect recovery times. Before recruiting a patient, the doctor ensures that the patient is available to go, with the required timing, to the clinic, for the scheduled visits. This fact is underlined several times when providing study information to the patient.

Interruption and withdrawal of subjects from the clinical trial

Patients who miss the visits for two consecutive weeks, before/until the 14th week, and the patients who miss the visits for one week, after the 14th week, will be reached by phone by the Principal Investigator to assess their availability to go on with the study; in the event that the patient does not intend to continue with the visits at the centre, they will be excluded from the study. Also, the patient who will turn out to be absent for more than half of the sessions will be excluded as well.

Following the resignation or withdrawal from the study by a patient, their data collection form will be identified, scanned and archived.

If a patient withdraws from the study, the Principal Investigator or his delegate records the event in the Patient Identification Register and on the Data Collection Form and stores all documentation.

Monitoring plan of the clinical investigation

To guarantee the conformity with ICH/GCP guidelines, the Clinical Research Coordinator (CRC) will be responsible for the study to be carried out in full observance of the Standard Operating Procedures, of the Protocol and other written instructions.

The main responsibilities of the CRC are to ensure adherence to the Protocol, to make sure that the data are accurately and fully registered and reported and to verify that the Informed Consent was obtained and registered for each subject before the beginning of the study.

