The CRC will keep in touch and meet the Principal Investigator on a regular basis throughout the whole duration of the study. The CRC will be allowed to check the various documents (Data Collection Forms, CRF and other related documents containing original data) related to the study in order to verify the conformity with the Protocol and to ensure the accuracy of recorded data.

Quality assurance, control procedures, data management and record-keeping

All the information gathered during the Study will be considered strictly confidential. The patients' consent to the registration of personal data will be requested at the time of recruitment; nevertheless the data collection forms will contain the Identification Code of the patient and their date of birth only. In order to guarantee the correct traceability of all parties involved, the number of the Study and the naming of the Center will be included as well.

At the end of the Study, all data will be archived using the appropriate safety measures at the Coordinating Site for a minimum of ten years.

If a patient withdraws their consent to data processing, they will be immediately destroyed to ensure total confidentiality, in addition each investigator will keep a copy of the study's documentation for at least two years after its conclusion.

The Principal Investigator builds and is responsible for the updating and custody of the Patient Identification Register or Enrollment Register.

The Patient Identification Register includes personal data of patients who agreed to take part in the study, the identification number assigned to the patient, their illness, indication of the eventual exclusion from the recruitment with its justification and date of recruitment. The patient code is constituted by a three-digit number: the first one indicates the center's number, as stated in this protocol, and the other two are sequential numbers, starting from 01. Only the Principal Investigator and, at their discretion, the members of their team have knowledge of the identities of patients enrolled in the study.

Deviations from the clinical protocol

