80 patients will be recruited during the study; they will be randomized 1:1 to the standard treatment group and the EmoLED Protocol group. In the control group, which follows the standard treatment, patients will be visited twice a week. The EmoLED experimental Protocol group will undergo medical examination once a week; in this case, therapy will consist in the standard treatment plus EmoLED treatment.

This sample size is sufficient to compare the average rate of the injured area reduction, considering Student-T test for the comparison between independent samples, by establishing $\alpha = 0.05$, power level (1- β) = 0,8, under the assumption to have an area reduction rate after 16 weeks amounting to 50% in Group 1 (control group), a difference of 20% between Group 2 (experimental group) and Group 1, a standard deviation of averages equal to 50% of the mean values and a bilateral hypothesis.

Statistical analysis

The average rate of reduction of the injured area between the two groups will be compared using the Student-T-test, the quality of life in both groups at the baseline, after 16 weeks and the difference with the baseline will be compared using Student-T-test for independent samples.

Linear regression models will be used to value the differences between the groups to exclude any confounding factors. Due to the usually asymmetrical nature of cost distribution, the comparison of the costs related to the treatment and control group, in both the NHS and society perspective, will be made using the non-parametric Mann-Whitney U test.

Generalized linear regression models will be used to value the differences between the groups to eliminate any confounding factors.

The cost-effectiveness of both treatments in the time frame of the study (16 weeks) will be valued by calculating the incremental cost-effectiveness ratio (ICER) and expressed in terms of incremental costs for "quality adjusted years (QALY).

Extrapolations of results about the cost-effectiveness that simulate longer time-frames will be made considering decision-making models (e.g. Markov models) and eventually including the data gathered during the study with literary data and/or evidence from other studies.

Data publication policy

L.U.C.E. Study Protocol version 3.0 (24/02/2020)

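### Randomised patients can be excluded for low attendance or for not continuing, and the plan has no analysis population or missing-data method that keeps them in the comparison

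*Combined protocol and SAP*

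**What the plan says.** Under *Interruption and withdrawal of subjects from the clinical trial*, a randomised patient can be excluded by two routes.

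- **Not continuing.** Patients who miss two consecutive weeks up to week 14, or one week after that, are phoned by the investigator and asked whether they can carry on. For those who will not, the text reads: "in the event that the patient does not intend to continue with the visits at the centre, they will be excluded from the study".
- **Low attendance.** "Also, the patient who will turn out to be absent for more than half of the sessions will be excluded as well".

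The same section has the withdrawn patient's form scanned and archived, and the investigator or a delegate "records the event in the Patient Identification Register and on the Data Collection Form and stores all documentation". Data are destroyed in one case only, given in the section on quality assurance and data management: "If a patient withdraws their consent to data processing, they will be immediately destroyed".

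*Statistical analysis* sets the primary comparison: "The average rate of reduction of the injured area between the two groups will be compared using the Student-T-test". It adds regression models for confounding, a Mann-Whitney test for costs and an ICER. It names no analysis population, missing-data method or sensitivity analysis for patients who leave. *Calculation of the sample size* states no dropout allowance.

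Three other places matter. *Measurable parameters* plans 32 visits in Group 1 and 16 in Group 2. *Objectives of the study* lets observation end at week 16 or sooner, without giving a reason. *Image Acquisition* measures the area at the start, middle and end of treatment.

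**The concern.** Randomisation protects the comparison only while patients are compared as allocated. Both exclusion routes depend on behaviour after allocation, and that behaviour could plausibly differ between the arms, because one arm is asked to come twice as often. It could also relate to outcome. Under *Known or predictable factors*, the protocol says: "Discontinuity of patients can affect recovery times". If low attenders heal less well, and their number or type differs by arm, leaving them out moves the week-16 difference for reasons unrelated to treatment. Regression for confounding cannot restore patients who are absent from the data set. If the choice is not written down, it may be made after the results are known.

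**Working it through.** **1. The plan's own sample size.** Inputs from *Calculation of the sample size*: control mean 50%, difference 20%, two-sided alpha 0.05, power 0.80, and "a standard deviation of averages equal to 50% of the mean values". Reading 20% as percentage points (pp), the means are 50 and 70 and the SDs 25 and 35, so the pooled SD is √((25² + 35²)/2) = √925 = 30.4. By the normal formula, n per arm = 2 × (1.960 + 0.842)² × 925 / 20² = 36.3, so 37; the t-test needs 38. With 40 per arm, power is 0.83 (0.84 with a common SD of 30). On this reading 80 patients are sufficient if all are analysed.

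**2. The attendance cut-offs, counting planned visits.** In Group 1, more than 16 of 32 missed means at most 15 attended. In Group 2, more than 8 of 16 missed means at most 7 attended.

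**3. Effect of exclusion on the group difference.** Let e be the share excluded in an arm, and d the pp by which excluded patients' area reduction falls short of that of patients kept. Then arm mean = (1 − e) × kept mean + e × (kept mean − d), so kept mean = arm mean + e × d. The shift in Group 2 minus Group 1 is e₂d₂ − e₁d₁. It is zero if e and d are equal across arms.

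**4. Equal attendance in both arms.** The documents give no attendance figures, so the rates and d = 20 are assumptions. For independent misses at attendance q, the shares are P(Bin(32, q) ≤ 15) and P(Bin(16, q) ≤ 7). For attendance that clusters by patient, a beta-binomial with mean 0.80 and within-patient correlation ρ is used.

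| Assumption | Group 1 excluded | Group 2 excluded | Shift, pp |
|---|---|---|---|
| Independent, 80% | 0.0% | 0.1% | 0.03 |
| Independent, 70% | 0.5% | 2.6% | 0.4 |
| Independent, 60% | 9.2% | 14.2% | 1.0 |
| Clustered, mean 80%, ρ = 0.2 | 8.1% | 8.2% | 0.01 |
| Clustered, mean 80%, ρ = 0.3 | 11.9% | 11.6% | −0.05 |

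The clustered rows mean about 3 to 5 of 40 patients per arm (0.081 × 40 = 3.2; 0.119 × 40 = 4.8), with almost no shift.

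**5. Exclusion in one arm only.** Take 10% excluded in one arm, none in the other, and d = 20. The shift is 0.10 × 20 = 2 pp, so a true difference of 20 is estimated as 18 (Group 1 excluded) or 22 (Group 2 excluded). With 36 against 40 patients and SD 30, power is 0.73 or 0.88, against 0.84 with all 40 kept and measured. The smaller number alone, without bias, gives 0.82. With no true difference and SD 25, type I error is about 6%.

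**6. Precision, apart from bias.** Power for a 20 pp difference, noncentral t:

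| Patients per arm | SD 30 | SDs 25 and 35 |
|---|---|---|
| 40 | 0.838 | 0.828 |
| 38 | 0.818 | 0.808 |
| 37 | 0.808 | 0.797 |
| 36 | 0.797 | 0.786 |
| 32 | 0.747 | 0.736 |

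Power stays at 0.80 after a loss of 3 per arm (SD 30) or 2 per arm (SDs 25 and 35).

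**The case against.** The best reply is that the section concerns participation, not analysis. A reader might infer that the plan prescribes a completers-only comparison. The documents do not support that: forms are kept, documentation is stored, and destruction follows only withdrawal of consent to data processing. This stands, and it limits the point to what the plan permits. It does not answer it, because nothing tells the analyst to keep these patients.

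A reader might also infer that 32 against 16 sessions makes the rule itself unbalanced. The threshold is the same proportion in both arms, and at equal attendance it creates little imbalance, almost none once attendance clusters by patient. Bias needs attendance, or the kind of patient excluded, to differ by arm. The one-arm illustration simply assumes this, and no document supports its inputs.

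The protocol also has safeguards. Availability is checked before recruitment and absentees are phoned. In Group 2, at most 7 of the first 14 weeks can be missed without two in a row, so anyone missing more than 8 of 16 would have been called. These steps should reduce the numbers, but they do not say how the remaining patients are analysed.

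**Conclusion.** The point holds as a gap with a practical consequence: an analysis selected on post-randomisation attendance follows the plan as written. The possible bias in the week-16 comparison has unknown direction and size. It is at most about 1 pp in the equal-attendance illustrations, 2 pp under the assumed one-arm exclusion, and near zero if attendance is good. All of these rest on assumed attendance and d = 20; the power figures also rest on reading 20% as percentage points.

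Two further inferences go too far.

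- **Costs.** One might say that the rule selects on part of the cost outcome, since visits are a listed cost. But the *Data Collection Form* section collects costs by questionnaire at the first visit and takes that visit as the reference for adherence costs. How missed visits enter the cost outcome is unclear, so selection is possible but not shown.
- **Sessions.** One might say that it is open whether sessions means visits or weeks. *Measurable parameters* numbers the planned visits, so visits is the natural reading. What is open is whether they are counted as planned or as due, because observation may end early.

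**What to change.** In *Statistics*, state that the primary analysis includes all randomised patients in their allocated group, and that data already collected are used unless consent to data processing is withdrawn. In the interruption and withdrawal section, state that exclusion from the study does not remove a patient from the analysis, and whether sessions are counted as planned or due.

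Pre-specify one method for week-16 areas missing through dropout or exclusion. It should use the baseline and mid-treatment areas already measured; multiple imputation is one option. Where observation ended early as planned, use the end-of-treatment area and do not impute it. Use any attendance-based set only as a sensitivity analysis.

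This needs no extra patients, visits or measurements and does not change who continues treatment. The estimate will include poorly adherent patients and may be slightly diluted. Imputation from at most two earlier areas recovers only part of the lost precision. An amendment may be needed, and the protocol's section on amendments suspends the trial until ethics approval if it is substantive.

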As further detailed in the section on statistical analysis, it is expected to register, during the time of observation, a difference in efficacy between EmoLED protocol group ("Group 2") and SOC protocol group ("Group 1"), in terms of "healing rate", intended as a reduction of the wound area, but also as a progress, in a broad sense, of the overall clinical situation of the lesion, in terms of pain and quality of life.

Endpoint

Primary endpoint of the study

The primary endpoint will be the outcomes comparison in terms of healing rate of lesions treated with SOC only versus lesions treated with EmoLED and SOC, on week 16th.

L.U.C.E. Study Protocol version 3.0 (24/02/2020)

Secondary endpoint

- 1) Safety of treatment
- 2) Evaluation of the healing time of the lesions treated with the standard method (Group 1) versus the lesions treated with the EmoLED Protocol (group 2);
- Evaluation of the treatment of chronic ulcers in patients undergoing standard treatment versus EmoLED treatment about life quality (QoL) in 16 weeks, through generic questionnaires as the EuroQiL-5D2 and specific questionnaires as the Wound-Qol3;
- 4) Evaluation of costs related to the treatment and control group, in both the NHS and society perspective
- 5) Evaluation of VAS scale in both groups;
- 6) Evaluation of satisfaction, complexity and helpfulness of EmoLED device, considering both the perspective of patients, and the one of doctors and health care workers involved;
- 7) Evaluation of cost-effectiveness using EmoLED for the treatment of ulcers.

Measurable parameters

The key data and lesion's pictures of each patient will be collected in the Data Collection Form, after the enrollment and the signature of the Informed Consent:

- Group 1: V1 (Visit 1 and first treatment), V2, V3, V4... until V32 (32 treatments are planned during 16 weeks, 2 per week)
- Group 2: V1 (Visit 1 and first treatment), V2, V3, V4... until V16 (16 treatments are planned during 16 weeks, 1 per week)

The parameters used to define the study result will be found through:

- Photographic images of lesions treated with EmoLED and control lesions
- Data Collection Form filled by the medical staff during the visit
- Economic/organizational impact survey
- Medical/clinical/social impact survey
- Survey on the usability of the device
- Detection of pain through VAS scale

Registration of clinical data

The data related to the evaluation of the study endpoints are acquired, for both groups, during the visits.

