In the case of isolated deviations from the protocol, these are registered in the data collection form, which is provided with a space to record any variation or comment the doctor deems appropriate. In case, during the study, a modification to the protocol is deemed necessary, the investigator communicates this need to the sponsor, who convenes the investigator of the coordinator centre, the study coordinator and any other experts in the field, and discusses the proposed variations and, where appropriate, submits a request for amendment to the Ethics Committees to approve the changes deemed necessary.

Adverse Events

Despite all the information in our possession and physical characteristics and performances of the device that do not suggest the possible occurrence of and adverse event, this section of the Protocol takes into consideration the possibility that said event could take place.

An Adverse Event (AE) is any untoward change in the state of health, or side effect, or unexpected benefit that could occur in a patient involved in in a clinical study while they receive the treatment or within a given timeframe following the conclusion of the therapy, not necessarily related to said treatment or clinical experimentation. An AE can consist in any unfavourable and/or unexpected sign or symptoms (including abnormal results from laboratory testing) or a pathology temporarily associated with the use of a medicinal product (subject of the experimentation) or experimental device, that whether or not is related to that medicinal product or device.

The morbid condition of each patient will be monitored the whole time of the study. During each visit any sign manifested by the patient will be carefully observed, in fact, the subject will be encouraged to report any symptom with direct questions, such as: "How have you been feeling since our last visit?". They will also be prompted to spontaneously report any adverse events that occurred during the study.

Any significant clinical anomaly encountered over the course of the study will be monitored and observed until its normalisation, or until it will be clinically explainable.

Serious Adverse Events

L.U.C.E. Study Protocol version 3.0 (24/02/2020)

A Serious Adverse Event (SAE) is defined as any unfavourable medical occurrence that, at any dosage, will result in any of these consequences:

- Death of the patient
- Any inauspicious outcome in the short term

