- Hospitalization or prolonged hospitalization of the subject
- Disability or significant/persistent incapacity
- Other major medical event

Other medical events that do not involve the death of the patient, or do not endanger their life, or do not require the hospitalization of the subject can be also classified as SAE when, according to proper medical assessment, they may constitute a risk for the subject or they may require medical intervention or surgery to prevent one of the outcomes previously described.

Hospitalization is defined as the eventuality in which the subject is withheld (usually for at least a night) in hospital or in the emergency room for observation and/or treatment. Whenever is questioned if the hospitalization took place or if it was necessary, the adverse event must be considered serious. It is not necessary to consider as an Adverse Event a hospitalization due to elective surgery or due to the implementation of routine clinical procedures that are not consequences of an Adverse Event. If during the procedure an unfavourable eventuality is reported, it shall be considered as an Adverse Event, if Serious or not it will be decided according to customary criteria.

Reporting of Adverse Events or Serious Adverse Events

All the Adverse Events reported by the subject or observed by the Ricercatore or by members of their teamwill be mentioned on the SAE form.For each Adverse Event

must be gathered the following information:

- Date and Time of insurgence and resolution (duration)
- Extent (further defined in the text)
- Treatment eventually requested or measures taken
- Outcome
- Relation with the product used in the experimentation (further defined in the text)
- If the Adverse Event caused the subject to withdraw from the study

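### Adverse events are sought at every visit, with up to 32 visits planned in Group 1 and 16 in Group 2, so any between-group comparison of non-serious events rests on unequal ascertainment

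*Combined protocol and SAP*

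**What the plan says.** **Visits.** Under Measurable parameters, Group 1 runs "until V32 (32 treatments are planned during 16 weeks, 2 per week" and Group 2 runs "until V16 (16 treatments are planned during 16 weeks, 1 per week". Both are maxima: Objectives of the study allows observation to end before week 16, and then adds one follow-up visit 4 weeks later.

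**How adverse events are found.** The Adverse Events section says "During each visit any sign manifested by the patient will be carefully observed", and adds that "the subject will be encouraged to report any symptom with direct questions, such as: 'How have you been feeling since our last visit". It also provides for unprompted reports: "They will also be prompted to spontaneously report any adverse events that occurred during the study". The reporting section covers "All the Adverse Events reported by the subject or observed by the Ricercatore" or by the team, with dates of onset and resolution.

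**Safety as an endpoint.** The first secondary endpoint is "Safety of treatment", with no measure attached. The Statistics section contains no safety analysis.

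**What is absent.** No section puts the two groups on the same schedule for eliciting adverse events, blinds their assessment, or accounts for the number of contacts.

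**The concern.** Group 1 is planned to be examined and questioned twice as often as Group 2, over recall intervals half as long. If true event rates were equal, short-lived local signs and minor symptoms would tend to be recorded more often in Group 1 simply because someone looked more often. A table of adverse events by arm could then make the once-weekly EmoLED regimen look as safe as, or safer than, control for reasons unrelated to the device.

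Local signs are the most exposed. Under Medical and surgical procedures the lesion lies beneath a foam dressing and a double-layer compression bandage, so a patient is unlikely to see redness or maceration between visits.

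Elsewhere the protocol does use timing common to both groups. Quality of life is collected at first and last visits and every 4 weeks, and lesion area is quantified at the beginning, middle and end. Adverse events follow the unequal visit calendar instead, and the section on factors that may impair interpretation does not mention it.

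**Working it through.** **1. The plan's own counts.** 2 visits × 16 weeks = 32; 1 visit × 16 weeks = 16. Both match the protocol; the ratio is 2.0. With the follow-up visit they become 33 and 17, a ratio of 33/17 = 1.94.

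**2. Assumptions.** The documents give no event durations, no recall figures and no spacing of the two weekly visits. I assume visits 3.5 days apart in Group 1 and 7 days apart in Group 2, onset uniform within the interval, and equal true event rates.

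**3. Signs seen at a visit, with or without later report.** A sign lasting *D* days is present at a visit with probability *p* = min(1, *D*/interval). If missed, it is reported at the next visit with probability *r*. The probability of a record is *p* + (1 − *p*)*r*.

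Example, *D* = 2 and *r* = 0.5:
- Group 1: 2/3.5 = 0.571; 0.571 + 0.429 × 0.5 = 0.786.
- Group 2: 2/7 = 0.286; 0.286 + 0.714 × 0.5 = 0.643.
- Ratio, Group 2 to Group 1: 0.643/0.786 = 0.82.

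| Duration (days) | Seen, Group 1 | Seen, Group 2 | Ratio, r = 0 | Ratio, r = 0.5 | Ratio, r = 0.8 | Ratio, r = 1 |
|---|---|---|---|---|---|---|
| 1 | 0.29 | 0.14 | 0.50 | 0.89 | 0.97 | 1.00 |
| 2 | 0.57 | 0.29 | 0.50 | 0.82 | 0.94 | 1.00 |
| 3.5 | 1.00 | 0.50 | 0.50 | 0.75 | 0.90 | 1.00 |
| 5 | 1.00 | 0.71 | 0.71 | 0.86 | 0.94 | 1.00 |
| 7 or more | 1.00 | 1.00 | 1.00 | 1.00 | 1.00 | 1.00 |

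The ratio never exceeds 1, because *p* in Group 2 is never above *p* in Group 1. It reaches 0.50 only when *r* = 0 and the sign lasts 3.5 days or less.

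**4. Minor symptoms known only by recall.** Let recall decay with half-life *h*, so *k* = ln 2/*h*. Mean recall over an interval *T* is (1 − exp(−*kT*))/(*kT*).

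For *h* = 7 days, *k* = 0.099 per day:
- Group 1, *T* = 3.5: *kT* = 0.347; 0.293/0.347 = 0.845.
- Group 2, *T* = 7: *kT* = 0.693; 0.500/0.693 = 0.721.
- Ratio 0.721/0.845 = 0.854, about 15% fewer records in Group 2.

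The half-life is an assumption, so here is the range. With *h* = 14 days, mean recall is 0.918 and 0.845, ratio 0.92 (8% fewer). With *h* = 3.5 days, it is 0.721 and 0.541, ratio 0.75 (25% fewer).

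**5. Serious or lasting events.** Deaths, hospitalisations and anything lasting 7 days or more should be captured almost equally, so the ratio is about 1.

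**The case against.** **No comparison is defined.** Endpoint 1 carries no comparative wording, unlike several of the other secondary endpoints, and the Statistics section has no safety analysis. This stands: the problem is conditional on a between-group comparison being made. In a randomised trial with safety among its stated purposes, one is likely, and the rule for it can still be set in advance.

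**Unequal contact is part of the regimen under test.** True. A real difference in events caused by visiting less often belongs in the comparison. A difference in how often events are noticed does not.

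**The plan already has safeguards.** The example question covers the whole gap since the last visit, spontaneous reports are prompted, resolved events can be recorded with dates, and both groups have the 4-week follow-up. These reduce the imbalance, and the overall effect is probably well below 2:1. They help least for signs hidden under the bandage.

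**Two stronger readings are tempting.** A reader might infer that Group 2 will record half as many adverse events. The documents do not support that: 50% requires no recall at all, for signs of 3.5 days or less, and the protocol actively seeks recall. A reader might also infer that the safety result will be tilted towards EmoLED overall. That is not established either. No blinding is described, the regimen is visible to patients and staff, and relatedness is graded against the study product. Closer attention to device-related events in Group 2 could push the other way, by an amount the documents do not let us calculate.

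**Conclusion.** The concern holds for non-serious events, in any between-group comparison made for secondary endpoint 1. Followed as written, the plan gives unequal detection by arm, at most 32 against 16 planned occasions before follow-up.

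Considered alone, visit frequency can only lower the Group 2 count:
- about nil for serious or lasting events;
- about 15% fewer records for recalled minor symptoms at an assumed 7-day half-life (8% to 25% for half-lives of 14 to 3.5 days);
- up to 50% only for short signs that the patient does not perceive or report.

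These sizes rest on evenly spaced visits, uniform onset and equal true rates. The true size is unknown, and the net direction after allowing for open allocation is not certain. This is a cheap improvement to make the comparison like-for-like; it is not a ground for doubting how individual events are recorded or reported.

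**What to change.** 1. Keep recording and reporting every event whenever it is found.
2. Designate one weekly visit in both groups. At it, ask the same question with a fixed 7-day recall and make the same wound and perilesional check. With the follow-up visit, each arm then has 16 + 1 = 17 planned comparable occasions.
3. On the Data Collection Form, mark whether each event was found at the weekly assessment, at the extra Group 1 visit, or spontaneously.
4. Add a safety paragraph to the Statistics section: compare groups on weekly-assessment events and on all serious adverse events, and show all-event totals and the number of contacts per arm beside them.

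**Cost.** One tick-box and some protocol wording; no extra visits or staff, and no change to treatment. If the change were classed as a substantive amendment, the protocol's own rule would suspend the trial until ethics approval, so timing matters.

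**Downside.** Non-serious Group 1 events found only at the extra visit leave the main comparison, though they stay in the totals and listings. Mid-week questioning in Group 1 may still prime recall at the weekly assessment, so some imbalance remains; the totals and contact counts let a reader judge it.
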